Title:

Comparison of placement of double-lumen endobronchial tube using Glide Scope with 2 different stylet configurations vs standard Macintosh laryngoscopy.

Principal Investigator:[name], Emory University School of Medicine

V. 03April2015

NCT02495259

Title: Comparison of placement of double-lumen endobronchial tube using GlideScope with 2 different stylet configurations vs standard Macintosh laryngoscopy.

Principal Investigator: [name]
Emory University School of Medicine
Department of Anesthesiology

Site: Emory University Hospital (EUH) and Emory University Hospital – Midtown (EUHM)

IRB: Emory University School of Medicine

Purpose of Study

To evaluate the technique of placement of the double-lumen endobronchial tube (DLT) using an included stylet that has been radically bent (ZU-bend) as compared to a commercial GlideRite stylet with the GlideScope and direct laryngoscopy using Macintosh laryngoscope.

Introduction

Placement of the DLT is viewed as more challenging partly due to bulkiness and a lack of flexibility that the DLT has compared to single lumen endotracheal tubes, as well as a larger and more fragile occlusion balloon that is more prone to rupture. Securing an airway using traditional laryngoscopy as well as video-assisted indirect laryngoscopy each has its unique advantages and disadvantages.

In a recent study comparing laryngoscopy with Macintosh blade and GlideScope the former was concluded to be superior with respect to intubation success (1), while an earlier study indicated GlideScope to be equivalent to direct laryngoscopy (4). A follow-up editorial pointed out that in Russel's study there was no inclusion of the GlideRite stylet designed specifically for use with GlideScope and DLT, possibly explaining difficulties with GlideScope-assisted intubations (2, 3).

In a small anecdotal sample, the use of a radically curved DLT stylet, the ZU-bend, and GlideScope appeared to be useful in placement of the DLTs by multiple anesthetists under supervision of one anesthesiologist ([name], presented at Thoracic Anesthesia Symposium 2015).

Therefore, we propose to merge the study protocol similar to Russel et. al. (1) with inclusion of both the suggestions from Bussier's editorial , as well as the experience with radically bent DLT stylet (ZU-bend) to evaluate each method with respect to intubation ease and to compare the complication rate with each technique.

Investigational Devices

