The intubation modalities (GlideScope, Macintosh laryngoscope, GlideRite stylet and DLT intubating stylet) have all been approved for clinical use and have been used routinely at our institution for DLT placement.

Macintosh blade is one of the most commonly used direct laryngoscopy blades for both single and double-lumen endotracheal intubations. It allows the practitioner to visualize larynx for subsequent intubation.

The **GlideScope** is a video laryngoscope that provides a real-time view of the airway and tube-placement during intubation in place of the direct laryngoscope.

The **GlideRite Rigid stylet** is specifically designed to work with the GlideScope video laryngoscope to facilitate intubation. It provides necessary rigidity and curvature to an otherwise flexible endotracheal tube to permit easier manipulation of it for tracheal intubation.

ZU-bend is a specific shaping technique of the intubating stylet that is more closely related to GlideScope blade curvature. There is a commonplace practice of shaping a flexible stylet for intubation to suit a particular combination of patient and equipment variables. The degree of shaping is somewhat specific to each provider, and is a normal procedure for using the intubating stylet. Bending of the stylet prior to intubation constitutes a routine preparation step for the majority of intubations. The steps for shaping of the stylet are provided in the appendix A.

Objectives

The current research does not provide clear support for one method or another in DLT placement techniques. Additionally, our research has shown that the ZU-bend stylet may be useful with the GlideScope. This randomized controlled study will compare the efficacy of three different methods of DLT placement.

The primary outcome measures will be the mean time it takes to place a DLT with each modality. Secondary outcome measures include success rate of first endobronchial intubation attempt; assessment of difficulty by the provider and complication incidence.

The end points of evaluation of each technique were selected based on Russel's protocol with our modification as summarized in Table 1:

Table 1.

Metric:	Defined as:
First intubation attempt success	DLT placed during initial laryngoscopy, within 120s
Duration of laryngoscopy	Time from laryngoscope at pt's lips through 1 st EtCO ₂ detection
Blood on device	Yes/No
SpO ₂ <96% during intubation	Yes/no
Voice changes	Evaluated in PACU - subjective answer by patient

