Lip trauma	Evaluated immediately post-intubation
Dental trauma	--/--
Sore throat	Analog pain scale 0-10, subjective answer in PACU
DLT cuff rupture	Loss of air pressure during procedure requiring >1 reinflation
Ease of device placement	Multi-question form to be filled by anesthetist after intubation
Overall ease of intubation	Subjective score 0-10; where 0 – worst, 10-best
Laryngoscope insertion	--/--
Glottic view	--/--
DLT delivery	--/-- placement of DLT mouth → into glottis proximity
DLT placement	--/-- ease of placing DLT through glottic opening

Study design and methods

This is a prospective, randomized, three-armed trial to investigate the efficacy of a radically curved DLT stylet to facilitate GlideScope-assisted tracheal intubation (Group 1) as compared to the commercial standard of GlideScope with GlideRite stylet (Group 2) and a direct laryngoscopy with Macintosh blade and a regular DLT stylet (Group 3).

This study will not impart additional risks on the patient in excess of those routinely cited for placement of the double-lumen endobronchial tube. All of the modern intubation modalities will be available at the intubation time, arguably decreasing the risk of an ultimately failed securing of patient's airway.

Following informed consent, each subject will be identified via a unique alpha-numeric code and randomized to either of 3 initial DLT placement technique groups. In all cases, the other 2 intervention modalities will be available in the event of failed 1st attempt intubation and will be used at practitioner's discretion. Patient's medical history and detailed airway exam will be recorded on the study form, including Mallampatti score, thyromental distance, ability to prognathize the mandible, any limitation in neck flexion/extension, any evidence of poor dentition or pre-existing dental damage, patient's height, weight and BMI.

Patient will then be taken to the operating room and anesthesia will be induced in the standard fashion per provider's discretion after denitrogenation of patient with 100% O₂ until EtO₂ value is greater or equal to 80%.

Laryngoscopy with the specified randomization modality will be performed by the anesthetist or fellow with timing of intubation recorded as described above. DLT size used will be recorded on the form as well.

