The placement of DLT will be verified in a standard fashion using fiberoptic bronchoscopy, auscultation and capnometry. The anesthetist/fellow then will complete their experience questionnaire portion of evaluation. After the conclusion of the procedure, patient will be extubated using standard ASA guidelines and taken to the Post-Operative Admission Unit (PACU), where the final evaluation of patient will take place, assessing voice change and throat pain as described above. This will conclude our study period and patient care will be resumed.

Human Selection Criteria

We plan to enroll up to 130 subjects in order to achieve 120 evaluable subjects with 40 in each arm at Emory University Hospital (EUH) and Emory University Hospital Midtown (EUHM). We will include patients that are scheduled for a thoracic surgical intervention in which surgeon requests lung isolation, including but not limited to: VATS, open thoracic surgery for lung or esophageal disorder, thoracic duct intervention, sympathectomy procedure.

Inclusion Criteria

- Male and female patients requiring DLT placement for their surgery at EUH or EUHM
- Patients willing and able to provide written informed consent

Exclusion Criteria

- Patients in whom a previously difficult airway manipulation was recorded on an anesthetic record.
- Lung transplantation procedures, as underlying pulmonary disorder will confound SpO₂ metric.
- Any patient who is receiving anticoagulants in excess of a daily aspirin, patients with INR >1.4
- Patients in whom one lung ventilation or placement of DLT is contraindicated.
- Patients who require a rapid-sequence intubation.
- Patients undergoing emergency procedures.

Patients who meet eligibility based upon the above criteria will initially be screened by the study team in concert with the patient care team. The study design will be explained to the patient and their interest assessed. Sufficient time will be allotted for the patient to discuss the study in detail with a study investigator, read the informed consent, ask any questions, and sign the informed consent prior to performing the study protocol. This will permit final confirmation that the patients who are enrolled in the study do not have airway anatomy consistent with an expected difficult airway and therefore meeting exclusion criteria for this study.

Estimated time to completion of study: 24 months from enrollment of first subject.

Statistical Analysis

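### The ease form is not tied to the first attempt, so ratings of a rescue technique can enter the assigned arm's difficulty outcome

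*Combined protocol and SAP*

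**What the plan says.** Under Study design and methods, each patient is "randomized to either of 3 initial DLT placement technique groups". The same section states that "the other 2 intervention modalities will be available in the event of failed 1st attempt intubation and will be used at practitioner's discretion". Movement between study techniques within a patient is therefore foreseen.

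Table 1 defines ease of device placement by a single instrument: "Multi-question form to be filled by anesthetist after intubation". Its items (overall ease, laryngoscope insertion, glottic view, DLT delivery, DLT placement) share one scale, "Subjective score 0-10; where 0 – worst, 10-best". The last item is the "ease of placing DLT through glottic opening". The procedure gives the order of events as laryngoscopy with the randomised technique, then verification of tube position, and then: "The anesthetist/fellow then will complete their experience questionnaire portion of evaluation".

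Table 1 also lists "Blood on device" as a yes/no item, with no device or attempt named. First-attempt success, by contrast, is tied in the same table to the initial laryngoscopy and a 120-second limit.

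Provider-assessed difficulty and complications are secondary outcomes (Objectives). The Statistical Analysis section names tests only. It gives no analysis set and no rule for patients who change technique.

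**The concern.** The Introduction sets out to evaluate each method for ease of intubation and to "compare the complication rate with each technique". That needs an ease score that belongs to the assigned technique. In a patient who crosses over, every item on the form has two possible referents, and the form is completed when the tube is already in by whichever technique worked. For passage through the glottis, the rescue may be the only completed passage there is to rate.

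The ambiguity does not fall evenly. It arises only where the assigned technique failed, so any replacement of scores is concentrated in the arm with more crossovers and tends to narrow a real difference in difficulty. Groups 1 and 2 share the GlideScope and differ in the stylet, so tube delivery and placement are the items where a stylet effect should show, and these are exposed. A first-attempt rating that was not collected at the time cannot be recovered reliably at analysis.

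**Working it through.** **The plan's own figures.** There is none for ease: no expected score, SD or first-attempt failure rate. The 40 per arm cannot be reproduced either, because no alpha, power, effect size or SD is stated. Everything below is illustrative, and all scores, rates and SDs are assumed.

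**1. Effect on mean ease.** Let f be an arm's first-attempt failure rate, and c the share of failures that cross over and are scored on the rescue. Assume a score of 7 after success, s = 2 for a failed assigned technique and r = 7 for a rescue.

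Recorded mean = (1 − f) × 7 + f × [(1 − c) × s + c × r]

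| Scored on rescue | Arm with f = 10% | Arm with f = 30% | Difference |
|---|---|---|---|
| c = 0 (assigned technique rated) | 6.3 + 0.1 × 2 = 6.50 | 4.9 + 0.3 × 2 = 5.50 | 1.0 |
| c = 0.5 | 6.3 + 0.1 × 4.5 = 6.75 | 4.9 + 0.3 × 4.5 = 6.25 | 0.5 |
| c = 1 | 6.3 + 0.1 × 7 = 7.00 | 4.9 + 0.3 × 7 = 7.00 | 0 |

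Each arm is inflated by f × c × (r − s), that is, by its crossover rate times the gap between rescue and failed scores. With a common c, the difference lost is c × (r − s) × (0.30 − 0.10). A smaller gap loses less: with r − s = 2 and c = 1 the loss is 2 × 0.20 = 0.4 point. At failure rates of 10% vs 20% and r = 7, the true difference is 6.5 − 6.0 = 0.5 point. All of it is lost at c = 1 and half (0.25) at c = 0.5.

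**2. Effect on power for ease.** At 40 per arm, two-sided 0.05 and 80% power (both assumed), the detectable standardised difference is (1.960 + 0.842) × √(2/40) = 0.626. With an assumed SD of 2.5 this is 0.626 × 2.5 ≈ 1.57 points. Take that as the true first-attempt difference and a gap of 4 points. The loss is c × 4 × (difference in failure rates).

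| Failure rates | Loss, c = 1 | Power | Loss, c = 0.5 | Power |
|---|---|---|---|---|
| 10% vs 5% | 0.2 | 69% | 0.1 | 75% |
| 20% vs 10% | 0.4 | 55% | 0.2 | 69% |
| 30% vs 10% | 0.8 | 28% | 0.4 | 55% |

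With c = 0 the power stays at 80%.

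**3. Blood.** Assume first-device rates of 40% vs 15%, a rescue-device rate of 15%, every failure crossing over, and blood independent of failure. With the first device scored, power at 40 per arm is 72% (normal approximation; the planned Fisher's exact test would differ somewhat).

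- Last device only: rate = (1 − f) × p + f × 0.15. The 40% arm falls to 37.5%, 35.0% or 32.5% at f = 10%, 20% or 30%, and the 15% arm stays at 15%. Power is 63%, 54% or 45%.
- Any device: rate = p + (1 − p) × f × 0.15. The rates become 41–43% vs about 16%, and power is 72–75%.

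So the blood item is sensitive to the missing definition mainly if only the last device would be scored.

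**The case against.** The timing of a form does not settle what it rates. The procedure describes laryngoscopy with the randomised technique, then verification, then the questionnaire, with no rescue step in between, and Table 1 is introduced as evaluating each technique. An operator could well rate the assigned technique, and the bias is then nil. The form itself is not reproduced, so its heading is unknown. This stands as a reason not to call the bias certain. It does not close the gap, because nothing in the documents tells the operator which attempt to score.

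Failure is also not the same as crossover. A tube placed after 120 seconds in the same laryngoscopy counts as a failed first attempt with no second device, and the discretion given to the practitioner does not exclude repeating the assigned technique. A rescue in a patient who has just had a failed attempt may be scored below an easy first success, and overall ease may be read as covering the whole episode. All of this stands, and is why the illustration varies c and the score gap.

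Finally, these are secondary outcomes, and first-attempt success is anchored to the initial laryngoscopy, so a technique's failures stay visible. That limits the damage but does not make the ease comparison interpretable.

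A reader might infer that blood caused by a rescue device is charged to the assigned one. The documents do not say whether the first, last or any device counts. If any device counts, the arm comparison hardly changes.

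**Conclusion.** The point holds as a gap in data collection that should be fixed: ratings of a rescue technique can enter the assigned arm's secondary difficulty outcome, in proportion to that arm's crossover rate. Analysis by randomised arm is not the fault. The fault is that the ease form names no attempt.

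The size is unknown. On the assumed scores and failure of 10% vs 30%, the recorded difference runs from the full 1.0 point, through 0.5, to 0, depending on whether none, half or all of the failures are scored on the rescue.

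A reader might infer more: that rescue results necessarily enter the assigned arm, or that the difference in difficulty disappears. The documents do not support either. That there is only one form, and that it follows the final attempt, are inferences from Table 1 and the order of the procedure. No analysis set is given, so crossed-over patients might be analysed by assigned arm, by technique used, or not counted as evaluable. Complete loss needs every failure to cross over and to be scored as highly as a first-attempt success. The blood item is a minor part of the point.

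**What to change.** - Head the ease form: score the first attempt with the randomised technique. Add a separate optional block for any rescue technique, and analyse the first block by randomised arm.
- Pre-specify how items not reached on a failed first attempt are handled. For example, tube placement through the glottis could be given the worst score, 0, rather than left missing. Otherwise missing scores would collect in the very patients at issue.
- Report the number of crossovers per arm beside the ease and complication results.
- Record blood on the first device separately from blood on any later device, and state which is the Table 1 outcome.

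The cost is revised form wording, a short second block and a few extra entries in crossed-over patients. Airway management does not change.

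### Does the unlisted, undefined exclusion for expected difficult airway anatomy leave eligibility or the randomised comparison unsound?

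*Combined protocol and SAP*

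**What the plan says.** Under Exclusion Criteria the protocol lists six bullets. The first is the only one about airway difficulty: "Patients in whom a previously difficult airway manipulation was recorded on an anesthetic record". The others cover lung transplantation, anticoagulation or a raised INR, contraindication to one-lung ventilation or to the double-lumen tube, rapid-sequence intubation, and emergency surgery.

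The paragraph below the list describes the route into the trial. It begins "Patients who meet eligibility based upon the above criteria will initially be screened by the study team", working with the clinical team. The patient then discusses the study and must "sign the informed consent prior to performing the study protocol". The paragraph ends by presenting these steps as a last check that those entering the trial "do not have airway anatomy consistent with an expected difficult airway and therefore meeting exclusion criteria for this study".

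Study design and methods gives the order of allocation: "Following informed consent, each subject will be identified via a unique alpha-numeric code and randomized" to one of the three techniques. Shortly afterwards it says: "Patient's medical history and detailed airway exam will be recorded on the study form". The items named there include the Mallampati score, thyromental distance, jaw protrusion, neck movement, dentition, height, weight and BMI. None is tied to eligibility.

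**The concern.** Read alone, the list admits a patient with unfavourable anatomy and no record of previous difficulty, whereas the narrative turns that patient away. A recorded past event and a prediction from anatomy are different tests, and the narrative speaks as if the second were already among the exclusions. The criterion also has no definition, although the same list gives a number elsewhere ("patients with INR >1.4").

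Two things could be at stake. The first is the population. Placement time is the primary outcome, with first-attempt success and provider-rated difficulty secondary, and anatomy plausibly bears on all three. A reader of the listed criteria alone would not know whether anatomically difficult airways were in or out.

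The second is more serious. The operator cannot be blinded to the device. If a loosely defined exclusion could be used once the allocation was known, patients might be removed selectively by arm. The airway examination is mentioned only after the randomisation sentence, so it is reasonable to ask whether the protocol leaves that door open.

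**Working it through.** No power, sample-size or effect calculation bears on this point. The check is a count and a reading of the sections side by side.

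**Count of the Exclusion Criteria bullets**

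| Feature | Bullets |
|---|---|
| Listed in total | 6 |
| Concern airway difficulty, by recorded history | 1 |
| Name or define expected difficult anatomy | 0 |
| Carry a numeric cut-off (INR) | 1 |

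The factual core therefore holds: the criterion appears only in the narrative and is undefined. The nearest alternative, the bullet on contraindication to the tube, is never linked to expected difficulty and cannot be relied on to cover it.

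**Do the list and the narrative contradict each other?** A contradiction would need one place that admits these patients and another that excludes them. The list is silent about them, and no sentence declares them eligible. The closing paragraph describes two successive steps: an initial screen on the listed criteria, then a final confirmation tied to consent. A patient who passes the first and fails the second is excluded. Someone following the whole section reaches one answer.

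**Is the missing cut-off unusual for this list?** Only 1 of the 6 bullets has a number, so 6 − 1 = 5 have none. At least two of those five, contraindication to the tube and need for rapid-sequence intubation, rest on clinical judgement. An airway criterion judged by an anaesthetist is of the same kind. The examination items in Study design and methods are described as data to be recorded, so their lack of thresholds says nothing about eligibility either way.

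**Can the exclusion act after allocation?**

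1. Human Selection Criteria ties the airway confirmation to the screening and consent step.
2. The same paragraph puts consent before any study procedure.
3. Study design and methods puts randomisation after consent.
4. Steps 1 to 3 place the airway decision before allocation.
5. The sentence on the airway examination has no time marker. It says where the findings are recorded, and its place on the page does not show that the examination follows randomisation.
6. Nothing under Statistical Analysis provides for dropping randomised patients because of their anatomy.

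The order is inferred from several sentences and not stated in one, but every timed statement points the same way.

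**Effect on the comparison.** If the exclusion is applied before allocation, it changes who enters and not how they are split between arms. If some such patients are enrolled because a screener used the list alone, randomisation balances them across arms in expectation. In either case the contrast between techniques remains valid.

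**The case for a change.** The strongest case for acting is that the repair is cheap and the ambiguity genuine. The paragraph itself screens on the criteria above it, and those do not contain the exclusion. Two hospitals recruit, and staff might apply an undefined rule differently. The confirmation step describes discussion, reading and signing but names no examination. In a trial where the operator sees the device, a discretionary exclusion should visibly be closed before allocation, and one sentence would do it.

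Part of this stands. The list is incomplete relative to the narrative, and the term is undefined, so judgement may vary between clinicians. A report that reproduced only the six bullets would describe the population imprecisely.

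The rest does not carry far. The protocol describes screening by the study team together with the clinical team, and nothing suggests that either hospital would work from the bullets alone. Divergence between sites is therefore conjecture. Removal after allocation is a possibility that the text does not exclude in so many words, but it runs against the order the text gives. A further sentence would record an order already inferable, and a definition would record a judgement the investigators have to make in any case.

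**Conclusion.** The observation is accurate but does not call for a change. It is an omission from a list, together with a criterion left to clinical judgement, and investigators and analysts can fill the gap sensibly by reading the section as a whole. Followed as written, the plan settles airway eligibility at consent and randomises afterwards, so the between-arm comparison is sound.

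The size is 0 of 6 listed exclusions naming the criterion. The number of patients affected cannot be computed, because the documents give no rate of expected difficult airway. No bias by arm and no effect on any endpoint is shown. The only consequence is for describing the population, and the airway findings recorded for each subject allow those actually enrolled to be described.

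This rests on two assumptions: that the confirmation is made where the protocol places it, at consent and before allocation, and that randomised patients are not later dropped from the analysis because of airway anatomy. The text supports the first and contains nothing against the second.

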The protocol in Russel's paper and previously cited data within their paper indicated that statistical significance can be attained at 30 subjects in each arm for 2 intervention comparison.

In our evaluation with 3 treatment arms, increasing sample size to 40 patients should provide adequate statistical power. Categorical data will be analyzed using Fisher's exact test. Mann-Whitney and Student's t-test will be applied where appropriate for continuous variables.

Adverse Event Reporting

The study team will comply with Emory University IRB policies for reporting adverse events. In this study, events that are determined by the Principal Investigator to be related to the research will be recorded and reported. Additionally, all deaths, related or unrelated, will be reported to the IRB. All events that are unanticipated problems that are related or possibly related to the research and place the subject or others at greater risk of harm than anticipated will be immediately reported to the Emory IRB.

Data and Safety Monitoring Plan

The data will be continuously analyzed to ensure there is not a significant trend that warrants early termination of the study. The PI will conduct monitoring after the first 10 patients are enrolled and again halfway through the study at 60 patients to evaluate for any related adverse events and ensure continued patient safety. Any serious complications encountered by the anesthesiologist in the room will be relayed to the principal investigator or co-investigators.

All investigators will complete the required training for conducting research at Emory University. All investigators will be made aware of the adverse event reporting policy and will report these events to the principal investigator in a timely manner.

References

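### Only two-group tests are named for the primary outcome of a three-arm trial, with no significance level, primary contrast or multiplicity rule: about 9% false-claim risk for the two stated contrasts and 12% for all three pairs, if each test uses 5% (assumed) and no technique differs

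*Combined protocol and SAP*

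**What the plan says.** The Objectives section sets the primary outcome: "The primary outcome measures will be the mean time it takes to place a DLT with each modality". The Statistical Analysis section assigns Fisher's exact test to categorical data, which leaves one sentence that covers placement time: "Mann-Whitney and Student's t-test will be applied where appropriate for continuous variables". It does not say when each test is appropriate.

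Four places bear on which arms are compared:

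- Purpose of Study sets ZU-bend "as compared to a commercial GlideRite stylet with the GlideScope and direct laryngoscopy using Macintosh laryngoscope".
- Study design and methods does the same, with Group 1 assessed "as compared to the commercial standard of GlideScope with GlideRite stylet (Group 2) and a direct laryngoscopy with Macintosh blade".
- Objectives is broader: "This randomized controlled study will compare the efficacy of three different methods of DLT placement".
- The title groups the arms differently: "using Glide Scope with 2 different stylet configurations vs standard Macintosh laryngoscopy".

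On size, the Statistical Analysis section reports from an earlier two-arm study that "statistical significance can be attained at 30 subjects in each arm for 2 intervention comparison". It then continues: "In our evaluation with 3 treatment arms, increasing sample size to 40 patients should provide adequate statistical power". The documents give no significance level, sidedness, power, effect size, standard deviation, primary contrast, testing order or multiplicity adjustment.

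**The concern.** Student's t-test and the Mann-Whitney test each take two groups, so three arms need at least two tests of the primary outcome under any of the descriptions above. Without an overall test or an adjusted level, the chance of at least one false positive exceeds the level of each test.

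A null result is plausible here: the Introduction cites conflicting earlier studies, and the Objectives say that research does not clearly favour any method. A false difference in placement time could be read as a reason to prefer one technique. Because no contrast is named as primary, the plan also gives a reader no way to tell which comparison was meant to be the main one.

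**Working it through.** **Inputs.** From the documents: three arms, 40 evaluable per arm, continuous primary outcome, two-group tests. Assumed, because the documents are silent: two-sided 5% per test, any significant contrast counts as a finding, one final analysis.

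**The plan's own figure.** Forty per arm cannot be reproduced, because no level, power, effect size or standard deviation is given.

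**Two contrasts sharing an arm (ZU-bend against each comparator), no true difference.** With equal arms the two test statistics have correlation 0.5. The critical value is 1.96.

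- P(at least one significant) = 0.05 + 0.05 − P(both significant).
- P(both significant) is about 0.0092 (simulated t-tests, 40 per arm).
- Result: 0.10 − 0.0092 = 0.0908. The bivariate normal calculation gives 9.07%.

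The title's pairing (each GlideScope arm against Macintosh) has the same structure and gives 9.0% in simulation.

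**All three pairs, no true difference.** At least one pair is significant when the range of the three means, in standard-error units, exceeds 1.96 × √2 = 2.77. The studentized range distribution for three means gives 12.2%, and simulated t-tests at 40 per arm also give 12.2%. With skewed times, Mann-Whitney tests give 8.7% (two contrasts) and 11.8% (three pairs).

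Treating the tests as independent would overstate the error: 1 − 0.95² = 9.75% and 1 − 0.95³ = 14.3%.

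**One arm truly different, the other two equal.** Only one pair is null, so the unadjusted error is 5.0%.

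**Error under the remedies, no true difference, normal times.**

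| Method | Three pairs | Two contrasts |
|---|---|---|
| Unadjusted t-tests | 12.2% | 9.0% |
| ANOVA at 5%, then t-tests at 5% | 5.0% | 4.1% |
| Bonferroni or Holm | 4.3% | 4.6% |

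With equal means but standard deviations in ratio 1:1:2 or 1:2:3 (assumed), the three-pair error is 6.0% for the ANOVA gate, 4.9% to 5.0% for Welch ANOVA followed by Welch t-tests, and 4.3% to 4.4% for Bonferroni.

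**Skewed times with unequal spread.** Log-normal times with equal means and log-scale standard deviations of 0.3, 0.3, 0.7 or 0.3, 0.5, 0.9 (assumed), three pairs:

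| Method | First case | Second case |
|---|---|---|
| ANOVA gate | 7.8% | 8.5% |
| Welch gate | 6.6% | 8.3% |
| Bonferroni t-tests | 5.8% | 7.5% |

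**What 30 to 40 could buy.** For 80% power, the sample-size ratio of a level of 0.05/3 to a level of 0.05 is (2.394 + 0.842)² / (1.960 + 0.842)² = 1.334, and 30 × 1.334 = 40.0.

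**Power at 40 per arm.** The documents do not say what power 30 per arm had, so three cases are shown. They correspond to differences of 0.652, 0.736 and 0.851 standard deviations (noncentral t). The ANOVA-gate ranges are for Group 1 against Group 3, with Group 2 placed from midway between them to equal to Group 3.

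| Power that 30 per arm had | 70% | 80% | 90% |
|---|---|---|---|
| Unadjusted 5% | 82% | 90% | 96% |
| ANOVA gate | 72–78% | 83–88% | 93–96% |
| Bonferroni, two contrasts | 74% | 84% | 93% |
| Bonferroni, three pairs | 68% | 80% | 91% |

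**The case against.** **The sample size was raised because of the third arm.** The plan ties the move to 40 to having three arms, and the ratio above matches a three-pair Bonferroni inflation at 80% power almost exactly. Multiplicity may well have been considered. But the stated reason is power and no adjusted level is written. A larger sample does not lower the false-positive rate of unadjusted tests. A reader might infer that multiplicity was ignored, or that it was handled; the documents support neither.

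**Twelve per cent is the wrong headline.** This largely stands. The Purpose and the design paragraph agree on ZU-bend against each comparator, and the design paragraph is the most specific text. The sentence in Objectives is a general summary and the title a label. Two contrasts, at about 9%, is the best-supported family, and 12% is the upper reading.

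**A win on both contrasts might be required.** If the claim were that ZU-bend differs from both comparators, no adjustment would be needed; under no true difference both tests are significant in only about 0.9% of trials. The plan states neither rule, so this is open.

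**The rate is conditional, and adjusting across separate techniques is partly convention.** Both points are fair. The inflation needs all three techniques to be equal and the 5% level is assumed. The missing level and primary contrast are defects whatever convention is followed.

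**The main comparison could be picked after seeing the data.** The plan does not prevent this, but nothing in it suggests an intention to do so. It could not raise the error above 12% for a given test, because the three pairs contain every reading.

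**Conclusion.** The point holds and should be fixed. The plan names only two-group tests for a three-arm primary comparison, and nothing in it controls the error across those tests. With two-sided 5% per test, any significant contrast counting, one final analysis and no true difference, the false-claim risk is about 9% for the two contrasts that the purpose and design text describe, and about 12% if all three pairs are tested. It is about 5% if one arm truly differs.

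Two stronger conclusions should not be drawn. The documents do not establish 12% as the trial's error rate, since testing all three pairs is only one permitted reading. Nor does any mean-based remedy guarantee 5%: the Welch version holds about 5% for roughly normal times, but skewed times with unequal spread took every mean-based option to about 6% to 9% in the cases simulated.

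**What to change.** In the Statistical Analysis section:

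1. State an overall two-sided 5% level.
2. Name the primary contrast or contrasts, and say whether a difference on any one of them is enough or all are required.
3. Name a single primary test of placement time, replacing the open choice between the t-test and Mann-Whitney.
4. Fix one rule for the family-wise error. Suitable choices are one-way or Welch ANOVA across the three arms, with pairwise tests only if it is significant; Holm or Bonferroni over the named contrasts; or one primary contrast with the others secondary.
5. If skewed times are expected, consider log time or a rank test and commit to it in advance. Say that the comparison is then no longer of mean time, and align the wording of the primary outcome.

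The cost is a few lines of text and no extra patients. The downside is pairwise power, as tabulated above. In the least favourable case shown (30 per arm meant 70%), three-pair Bonferroni takes 82% down to 68% and the ANOVA gate takes it to 72–78%. If 30 per arm meant 90%, the loss is from 96% to 91% at most. A single primary contrast keeps the unadjusted power but leaves the remaining comparisons secondary.
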